#### 10.5.8 Adverse Reactions

Adverse reactions are defined as solicited systemic, solicited local and Grade 3 unsolicited (AEs) considered as related to the trial vaccine according to the investigator.

#### 10.5.9 Adverse Events Related to Standardized MedDRA Queries

Subjects' AEs are filtered with Standard MedDRA Query (SMQ) for the following SMQs:

- Anaphylactic reaction (SMQ)
- Convulsions (SMQ)
- Embolic and thrombotic events (SMQ)
- Hypersensitivity (SMQ)
- Immune-mediated/autoimmune disorders (SMQ)
- Liver related investigations, signs and symptoms (Sub-SMQ)

In addition, two customized MedDRA queries are defined for taste and smelling disorder and events related to paraesthesia, hypoesthesia, and hyperesthesia.

---

The related terms are listed in the Appendix 4. The MedDRA SMQs for the specific terms are not included in the appendix. See official MedDRA documentation.

### 10.5.10 Credibility Interval and Estimate

The estimate, using  $\text{Beta}(\alpha, \beta)$ , is calculated as follows:

- $(\text{number of reactions} + \alpha) / (\text{total number of subjects} + \alpha + \beta)$ .

The lower and upper intervals are calculated as follows for a given number of reactions:

- Using SAS:  $\text{betainv}(0.025, \text{number of reactions} + \alpha, \text{total number of subjects} - \text{number of reactions} + \beta)$  and  $\text{betainv}(0.975, \text{number of reactions} + \alpha, \text{total number of subjects} - \text{number of reactions} + \beta)$ .

The SAS function `betainv` returns a quantile from the beta distribution.

## 10.6 Immunogenicity Assessments

If a subject receives a licensed/authorized vaccine, no further immunogenicity samples will be collected/analyzed after receipt of the licensed/authorized vaccine. Immunogenicity samples on Day 393 will only be collected from subjects who attend this visit at the site, ie, subjects who received the Day 180 booster AND who had not received a licensed/authorized vaccine before this visit.

### 10.6.1 Humoral Immune Response

In addition to evaluation of vaccine-induced immune responses, ELISA to SARS-CoV-2 N-antigen (not contained in the vaccine construct) will be performed to determine the subject's serology status to natural infection, to retrospectively identify the baseline serology status, and to detect and/or confirm natural infection during the trial. The SARS-CoV-2 N-antigen ELISA will be performed at the specified time points for humoral immune response testing to SARS-CoV-2 S-protein. See section 10.8 for more details related to censoring.

### 10.6.2 Seroconversion

Seroconversion is defined by a relevant increase in antibody titer compared to baseline. The titer is the highest dilution factor that still yields a positive reading for the antibodies. That is, larger titers correspond to larger concentration of antibodies. Depending on the type of antibodies and previous exposure of a subject to SARS-CoV-2 (as measured by antibodies to the SARS-CoV-2 N protein), different definitions of seroconversion will apply.

#### 10.6.2.1 SARS-CoV-2 RBD of S Protein Antibodies

In subjects who tested seronegative to the N protein for SARS-CoV-2 at baseline (see Section 10.6.3), seroconversion is defined as a fold increase above 1 in antibody titer against SARS-CoV-2 RBD of S protein.

In subjects who tested seropositive to the N protein for SARS-CoV-2 at baseline (see Section 10.6.3), the definition for seroconversion is a fold increase above 2 in antibody titer against SARS-CoV-2 RBD of S protein versus baseline.

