9.2.1 Humoral Immune Response

The humoral immune response elicited by the vaccine will be evaluated by measurement of SARS-CoV-2 spike protein-specific antibodies in serum by ELISA and SARS-CoV-2 neutralizing antibodies in serum by an activity assay.

In addition to evaluation of vaccine-induced immune responses, ELISA to SARS-CoV-2 N-antigen (not contained in the vaccine construct) will be performed to determine the subject's serology status to natural infection, to retrospectively identify the baseline serology status, and to detect and/or confirm natural infection during the trial. The SARS-CoV-2 N-antigen ELISA will be performed at the specified time points for humoral immune response testing to SARS-CoV-2 S-protein.

Seroconversion will be defined as:

- Subjects seronegative at baseline (in addition to a negative serostatus at baseline, such subjects would also not have been exposed to SARS-CoV-2 during the trial before the applicable sample was collected, as confirmed by a titer increase in antibodies to SARS-CoV-2 N-antigen or a RT-PCR-positive swab during the trial): an increase in antibody titer against SARS-CoV-2 spike protein versus baseline.
- Subjects seropositive at baseline: a 2-fold increase in antibody titer against SARS-CoV-2 spike protein versus baseline.

To further evaluate the humoral immune response, cross-reactivity with other viral antigens might be analyzed.

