### 10.6.3 Retrospective SARS-CoV-2 Serology Baseline Status and during the Trial

The retrospective SARS-CoV-2 status at baseline and throughout the trial is based on Anti-SARS-CoV-2 NCP ELISA (IgG) EI 2606-9601-2 G by Euroimmun.

Serology status for baseline:

- A ratio below 0.8 is defined as seronegative
- A ratio equal and above 0.8 and below 1.1 is a borderline case and will therefore also be defined as seronegative.
- A ratio equal and above 1.1 is defined as seropositive

If either the swab PCR performed at baseline is seropositive or the local ELISA serology assessment is seropositive, the subject is seropositive at baseline independently of the above cut-off values.

Serology status during the trial:

A subject categorized as seropositive at baseline will remain seropositive independently of later assessments, per the algorithm detailed for baseline assessment. A subject categorized as seronegative at baseline but assessed as seropositive at any post-baseline sample will be categorized as seropositive at this sample visit and beyond.

If either the PCR swab performed post-baseline or the local ELISA serology assessment collected post-baseline is seropositive, the subject is seropositive at that visit and beyond independently of the above cut-off values.

The baseline sample is defined as the sample taken at the screening/clinic visit 1 – day 1.

For subjects in which the retrospectively baseline/post-baseline serology status cannot be determined these will not be included in the counts of seroconverted subjects.

This definition is used throughout the endpoints for the sub-analysis.

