## 10.8 Censoring Rules for Subjects Unblinded and/or Treated with Alternate Licensed/Authorized Vaccine

Since the efficacy results from Trial CV-NCOV-004 are available and all subjects in this trial are currently eligible to receive a licensed/authorized vaccine, all subjects in this trial will be unblinded following protocol version 3.0. Hence, all subjects will be unblinded prior end of the trial, and their data will be censored in all analyses. The below rules are still applicable as subjects could request unblinding or became eligible to receive a licensed/authorized vaccine prior to the protocol V3.0.

The following censoring rules will be applied to these subjects to avoid any study bias.

- Subjects who are unblinded will be censored for the safety endpoints at the first day after unblinding. Any related follow-up data that is collected from censoring time point forward will be included in the listings output.
- Subjects who are unblinded but decide not to receive the alternate licensed/authorized vaccine and to stay in the study will be analyzed for immunogenicity as planned.
- Subjects who are unblinded, but decide to receive the alternate licensed/authorized vaccine, will have their immunogenicity data censored at the first day after receiving the alternate licensed/authorized vaccine. However, any related follow-up data that is collected from this time point forward will be included in the listings output.
- Subjects who received an alternate licensed/authorized vaccine without or before being unblinded will be censored for safety and immunogenicity at the first day after receiving the alternate licensed/authorized vaccine. As described above, data collected from the censoring timepoint forward will be included in the listings output.

This is summarized in Table 7.

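### The SAP's primary spike seroconversion rule drops, without declaring it, the protocol's condition that a baseline-seronegative subject was not infected during the trial before the sample

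*SAP*

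**What the plan says.** The proportion seroconverting for spike antibodies at Day 29 and Day 43 is a primary endpoint. Protocol 9.2.1 defines seroconversion separately by baseline serostatus. For baseline-seronegative subjects it adds that "such subjects would also not have been exposed to SARS-CoV-2 during the trial before the applicable sample was collected", and it names the evidence: "as confirmed by a titer increase in antibodies to SARS-CoV-2 N-antigen or a RT-PCR-positive swab during the trial". The sentence is clumsy, because it says non-exposure is confirmed by signs of exposure, but the intent is clear.

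For the same subjects SAP 10.6.2.1 states only that "seroconversion is defined as a fold increase above 1 in antibody titer against SARS-CoV-2 RBD of S protein". SAP 12.9.1 analyses any increase in baseline seronegatives and presents tables by baseline serostatus.

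SAP 10.6.3 does follow infection after baseline. A baseline-seronegative subject "assessed as seropositive at any post-baseline sample will be categorized as seropositive at this sample visit and beyond". Its only sentence about counting concerns unknown status: "For subjects in which the retrospectively baseline/post-baseline serology status cannot be determined these will not be included in the counts of seroconverted subjects".

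SAP 10.6.1 discusses detecting natural infection and then says "See section 10.8 for more details related to censoring". That section is titled "Censoring Rules for Subjects Unblinded and/or Treated with Alternate Licensed/Authorized Vaccine" and has no rule for infection.

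The exposure exclusion appears in the sensitivity analyses for the primary and secondary immunogenicity endpoints (SAP 9.4 and 12.9.3). SAP 6.1 declares two changes from protocol, on cell-mediated immunity and asymptomatic infection. The change history does not mention the seroconversion definition.

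**The concern.** Natural infection raises spike antibodies as vaccination does. The protocol therefore made absence of infection part of what seroconversion means in a seronegative subject. Under the SAP's rule a rise caused by infection counts as a vaccine response, which the protocol definition does not allow.

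A concrete case: Protocol 9.3 says a subject with confirmed infection should receive no further dose. The immunogenicity set needs only one dose, a baseline sample and one later sample. Such a subject, infected before Day 29 and sampled at Day 43, enters the primary Day 43 rate as a seroconverter.

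At stake is the meaning of a reported primary rate and its agreement with the protocol. The planned sensitivity analysis does not isolate the effect, because it also requires both doses, a sample after dose 2 and no relevant deviation.

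**Working it through.** **Text check: does any SAP rule remove a subject known to be infected before the sample from the primary rate?**

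| SAP place | What it removes | Removes known in-trial infection? |
|---|---|---|
| 10.6.2.1, 12.9.1 (definition) | nothing after baseline | No |
| 10.6.3 | undetermined status, from the seroconverter count | No |
| 10.8 | data after unblinding (safety) or licensed vaccine | No |
| 9.4, primary estimand | data after licensed vaccine | No |
| 12.9.1 (censoring) | data after booster | No |
| 9.4 and 12.9.3, sensitivity | exposed subjects, plus other restrictions | Yes, sensitivity only |

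Unknown status is taken out of the count while known infection stays in.

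**The plan's own figure.** With the Beta(1.9, 0.1) and Beta(0.5, 1.5) priors, the two design conditions at n = 200 require at least 194 seroconverters and at most 60 subjects with Grade 3 reactions. At 97.5% seroconversion and a 20% reaction rate:

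P(X ≥ 194) × P(Y ≤ 60) = 76.4%, against 76% stated. The figure reproduces.

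**Size of the inflation.** Let p be the rate under the protocol definition and q the share of baseline seronegatives infected before the sample. The documents do not give q; I assume 1–10%. I also assume every infected subject shows a rise and that infection is independent of vaccine response. Then

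SAP rate = p + (1 − p)q, so inflation = (1 − p)q.

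The denominator follows SAP 12.0, which presents both phases together: 90 + 200 = 290 CVnCoV 12 µg subjects per age group, as an upper bound. The half-width is half the 95% interval of Beta(k + 1.9, 290 − k + 0.1).

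| p | k | 95% interval | Half-width (points) | Inflation, q = 1% to 10% (points) | Share of half-width | Expected false seroconverters |
|---|---|---|---|---|---|---|
| 97.5% | 283 | 95.5–99.0% | 1.74 | 0.025–0.25 | 1–14% | 0.07–0.73 |
| 95% | 276 | 92.4–97.3% | 2.44 | 0.05–0.5 | 2–20% | 0.15–1.45 |
| 90% | 261 | 86.4–93.2% | 3.42 | 0.1–1.0 | 3–29% | 0.29–2.9 |
| 80% | 232 | 75.3–84.5% | 4.56 | 0.2–2.0 | 4–44% | 0.58–5.8 |

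Example: (1 − 0.95) × 0.10 = 0.5 points; 0.5 / 2.44 = 20%.

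**Planning illustration only.** Putting p + (1 − p)q into the n = 200 calculation moves 76.4% to 77.1% (q = 1%), 80.0% (5%) and 83.3% (10%). The trial does not use this as a decision rule.

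**Controls.** With 10 + 20 = 30 controls per age group, taken as all baseline-seronegative, expected infection-driven seroconverters are 30q = 0.3–3. The chance of at least one is 1 − (1 − q)^30 = 26.0% at q = 1% and 95.8% at q = 10%. Controls appear in the tables but are outside the primary humoral objective.

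**Precision after removal.** About 290 × 1% ≈ 3 to 290 × 10% = 29 subjects leave, so n = 287 to 261. The half-width goes from 2.44 to 2.46–2.61 points at 95%, and from 4.56 to 4.58–4.80 at 80%.

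**The case against.** The strongest case is that this is an incomplete cross-reference with little effect. SAP 10.6.2.1 does cite 10.6.3. Section 10.6.3 lets undetermined post-baseline status affect the seroconverter count, and it closes by saying its definition serves the sub-analyses throughout. The exposure exclusion is pre-specified as a sensitivity analysis, infections are tabulated (SAP 9.4, 12.9.5), immunogenicity data are listed, and the trial is descriptive. At the design rates of 95–97.5% the inflation is at most 0.5 points, and exclusion criteria 12 and 19 argue for a low q. The protocol sentence is awkward and does not say how to score an exposed subject. Removal also conditions on a post-vaccination event: if 5% of responders and 10% of non-responders were infected, a true 95% would read 95.5% unrestricted and 0.9025 / 0.9475 = 95.25% after removal; a true 80% would read 82.0% and 80.9%.

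Much of this stands on size. The effect is small when response is high, q is assumed, and removal is not free of bias if infection depends on response, although in that example it roughly halves the bias.

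It does not remove the mismatch. The citations of 10.6.3 in 10.6.2.1 concern baseline status, and the sub-analyses are defined by baseline status (SAP 9.0, 12.9.1). Removing infected subjects from numerator and denominator follows from the protocol placing the condition in the description of who belongs to the seronegative category. The infection tables bound the effect but do not show the rate without it.

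**Conclusion.** The concern holds. The SAP's primary spike seroconversion rule differs from the protocol's, no other SAP rule restores the missing condition for the primary analysis, and the difference is undeclared.

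The numerical effect is minor at the design rates of 95–97.5%: at most half a point. At 80% response with 10% infected it reaches 2.0 points, close to half the credibility half-width. These figures rest on the assumed 1–10% infected, on every infected subject showing a rise, and on independence of infection and response. The textual finding needs none of these. No hypothesis test depends on it. The sponsor should correct it because it concerns the definition of a primary endpoint, but it does not invalidate the trial.

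**What to change.** In SAP 10.6.2.1, and by reference in 12.9.1, add for baseline-seronegative subjects that seroconversion is assessed only while the subject is still seronegative under Section 10.6.3 at that sample visit. Subjects who have become seropositive leave numerator and denominator from that visit on. SAP 9.4 already uses this exclusion in its sensitivity analysis, and 12.9.3 already bases rates on the number available at each time point.

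Also:
- State how an N-antigen rise that stays below the 1.1 ratio is treated. It meets the protocol's evidence of exposure but not the cut-off in 10.6.3.
- Keep the unrestricted rate as a supportive table, so the effect of infection alone can be read off.
- Record in 6.1 and the change history that this restores the protocol's condition, and which definition the three interim analyses used.
- If the unrestricted rule is to stay primary, declare it in 6.1 as a change from protocol, with the reason.
- Optional: apply the same rule in 10.6.2.2. The protocol defines seroconversion only for spike, so this is for consistency.
- Minor: use one inequality for seropositive subjects. Sections 10.6.2.1 and 10.6.2.2 require more than a 2-fold rise; 12.9.1 says 2-fold.

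Cost: no new data. SAP 10.6.1 states "The SARS-CoV-2 N-antigen ELISA will be performed at the specified time points for humoral immune response testing to SARS-CoV-2 S-protein", and RT-PCR results are collected. The primary seroconversion tables need reprogramming. The change comes late, with three interims performed and the sponsor unblinded, so it must be documented openly, and results may differ from the interim tables. The precision loss is at most 0.17 points of half-width at 95% (2.61 − 2.44) and 0.24 at 80% (4.80 − 4.56), under the assumed infection range.

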## 10.2 Fold change from Baseline

Unless otherwise noted, fold change from baseline is defined as the ratio:

Post-baseline value/baseline value.

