## 10.3 Missing Data

Analysis of vaccination data will be done on a valid case basis, i.e., for missing observations, no imputation for missing data, such as last observation carried forward, will be applied. For nCoV spike protein antibodies and Virus Neutralization, concentration values marked as below the cut point (CP) will be set to 0.5\*CP.

No imputation of missing values will be done for any analysis (except the imputation for missing partial dates of AEs and concomitant medication). Reasons for discontinuation from the trial or trial vaccination will be listed and summarized.

Currently no replacement of drop-out subjects is foreseen.

For unsolicited AEs, solicited AEs occurring after Day 8 and concomitant medications, some missing or partially missing variables will be imputed as follows:

For AE or concomitant medication start date:

- If start date year value is missing, the date uncertainty is too high to impute a rational date. Therefore, if year value is missing, the imputed AE start date is set to missing.
- If start date year value is before the vaccination start date year value, started before the vaccination. Therefore:
  - If month is missing, the imputed start date is set to the mid-year point (i.e., 01JULYYYY).
  - If month is not missing, the imputed start date is set to the mid-month point (i.e., 15MONYYYY).
- If start date year value is equal to the vaccination start date year value, the start date month needs to be compared against the vaccination start date month, to determine the imputation rule to apply. Therefore:
  - If month is missing, the imputed month and imputed day is the same as start of vaccination
  - If month is lower than vaccination start date month and start date day is missing, the imputed start date is set to the mid-month point (i.e. 15MONYYYY).
  - If month is equal to the vaccination start date and start date day is missing, the start day will be set to the start day of vaccination.
  - If month is greater than the vaccination start date month and start date day is missing, the imputed start date is set to the beginning of the month (i.e., 01MONYYYY).
- If start date year value is greater than the vaccination start date year value, started after vaccination. Therefore,
  - If month is missing, the imputed start date is set to the year start point (i.e., 01JANYYYY).

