#### 10.6.2.2 SARS-CoV-2 Neutralizing Antibodies

In subjects who tested seronegative to the N protein for SARS-CoV-2 at baseline (see Section 10.6.3), seroconversion is defined as a fold increase above 1 in SARS-CoV-2 neutralizing antibody titer.

In subjects who tested seropositive to the N protein for SARS-CoV-2 at baseline (see Section 10.6.3), the definition for seroconversion is a fold increase above 2 in SARS-CoV-2 neutralizing antibody titer versus baseline.

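### Seroconversion is scored by N status rather than by the baseline titer in the assay concerned, so an N-seronegative subject with measurable baseline antibody counts as a responder on any higher reading

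*SAP*

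**What the plan says.** SAP 10.6.2 sets the intent: "Seroconversion is defined by a relevant increase in antibody titer compared to baseline". The operational rules then divide subjects by N-protein status alone.

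- N-seronegative, spike (RBD) ELISA, SAP 10.6.2.1: "seroconversion is defined as a fold increase above 1 in antibody titer against SARS-CoV-2 RBD of S protein".
- N-seronegative, neutralization, SAP 10.6.2.2: "seroconversion is defined as a fold increase above 1 in SARS-CoV-2 neutralizing antibody titer".
- N-seropositive, SAP 10.6.2.1: "the definition for seroconversion is a fold increase above 2 in antibody titer against SARS-CoV-2 RBD of S protein versus baseline". SAP 10.6.2.2 has the matching rule for neutralization.
- Protocol 9.2.1, for baseline-seronegative subjects and spike only: "an increase in antibody titer against SARS-CoV-2 spike protein versus baseline".

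Three other provisions matter.

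- SAP 10.2 defines fold change as "Post-baseline value/baseline value".
- SAP 10.3 says of both assays that "concentration values marked as below the cut point (CP) will be set to 0.5\*CP".
- SAP 10.6.3 decides baseline status from the N ELISA and says: "A ratio equal and above 0.8 and below 1.1 is a borderline case and will therefore also be defined as seronegative". A positive baseline PCR or local ELISA also makes a subject seropositive. A baseline RBD or neutralizing result does not.

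The proportion seroconverting at Day 29 and Day 43 is a primary endpoint for both assays (protocol 4.2.1, SAP 9.4).

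**The concern.** The any-increase rule does two different jobs. For a subject below the cut point at baseline it is a real criterion: the baseline becomes 0.5 × cut point, so a rise means reaching the cut point, which is at least 2-fold. For a subject who already has a measurable titer, it means only that the second reading exceeded the first. No margin for assay variation is set, and that does not secure the relevant increase that SAP 10.6.2 asks for.

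The plan asks for more than 2-fold where prior exposure is recognised, but it does not recognise it from the titer being scored. It allows such subjects to exist: recruitment is independent of serostatus (protocol 5.1), and borderline N ratios count as seronegative.

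The control arms are the most exposed, since hepatitis A and pneumococcal vaccines give no reason to expect a spike response. In the CVnCoV arms, a non-responder with a measurable baseline can be counted as a responder.

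**Working it through.** **1. The plan's own figure.** SAP 8.5.1 asks for at least 90% posterior probability that the seroconversion rate exceeds 95%, under a Beta(1.9, 0.1) prior. At n = 200 the smallest count x for which Beta(x + 1.9, 200 − x + 0.1) meets this is 194. The Grade 3 reaction condition, under Beta(0.5, 1.5), allows at most 60 events. With true rates of 97.5% and 20%, the product of the two binomial probabilities is 76.4%, which matches the stated 76%. With a true seroconversion rate of 95%, the probability of at least 194 of 200 is 12.4%, which matches the tabulated 12.

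**2. False response per visit.** Take a measurable baseline well above the cut point and no true change. The two readings are then exchangeable, so

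P(post > baseline) = (1 − P(tie)) / 2 ≤ 0.50.

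On a continuous scale there are no ties and the rate is 50% at any assay SD. An above-2-fold rule fires with probability 1 − Φ(1/(SD·√2)), SD in log2 units. SAP 10.7 describes titers as geometric means of duplicate dilutions, so ties will occur. The documents give neither the dilution step nor the SD. The duplicate columns below are simulated, assuming two-fold steps and a true titer placed at random within a step.

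| Assumed SD (log2) | >1-fold, continuous | >1-fold, duplicates | >2-fold, continuous | >2-fold, duplicates |
|---|---|---|---|---|
| 0.3 | 50% | 24% | 0.9% | <0.1% |
| 0.5 | 50% | 33% | 7.9% | 1.2% |
| 0.7 | 50% | 37% | 15.6% | 4.6% |
| 1.0 | 50% | 40% | 24.0% | 11.3% |

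The low-SD duplicate figures depend on where the titer sits: mid-step at SD 0.25 gives 8%. Titers just above the cut point also give lower rates.

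**3. Control arms.** Let d be the share of subjects who are N-seronegative with a measurable baseline. The documents do not give d; 1%, 5% and 10% are assumptions. The upper bound on false seroconversion is d × 0.5, that is 0.5%, 2.5% and 5.0%. Planned controls for the ELISA number 10 + 10 + 40 = 60, so the bound is 0.3, 1.5 and 3.0 subjects. Neutralization is measured only in the initial phase (protocol Table 1), which has about 20 controls, so the same bounds give 0.1, 0.5 and 1.0.

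**4. CVnCoV arms.** Suppose a true rate of 95%, d = 10%, and true failures spread evenly over subjects with and without a measurable baseline. The added false responders are 0.10 × 0.05 × 0.5 = 0.0025, so the observed rate is 95.25%. The n = 200 probability of reaching 194 moves from 12.4% to 15.8%. At d = 1% and 5% it moves to 12.7% and 14.0%.

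**The case against.** The best defence is that few subjects may be affected and that stricter results will be visible anyway. Protocol 6.2 excludes confirmed earlier COVID-19, earlier coronavirus vaccination and people at increased risk of exposure. Baseline PCR or local-ELISA positives already go to the above-2-fold rule, and a borderline N ratio does not prove a measurable RBD titer. SAP 12.9.1 also provides a 4-fold tabulation, geometric means, fold changes, individual plots and listings. The trial is descriptive, with no test between arms.

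Most of this stands, and it limits the weight of the point. It does not remove it. SAP 12.9.1 keeps any increase as the definition for seronegative subjects. The sensitivity set in SAP 12.9.3 excludes exposed subjects, but exposure is judged by the status algorithm of SAP 10.6.3, so N-negative subjects with a measurable titer can remain.

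A reader might infer something stronger, in three ways.

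- **A large gain in the sizing probability.** If 10% have a measurable baseline and 30% of those do not truly rise, inflation is 0.10 × 0.30 × 0.5 = 1.5 points. At 96.5% the n = 200 probability becomes 45%. With an overall true rate of 95%, the remaining subjects must then respond at (0.95 − 0.07)/0.90 = 97.8%. Subjects with existing antibody would fail at 30% against 2.2%, about 13 times as often. Nothing in the documents supports that. The sizing probability is also not an analysis decision rule.
- **A 67% false response rate.** This is the chance of firing at Day 29 or Day 43 on a continuous scale. The endpoints are per visit, so it corresponds to nothing that is reported.
- **A clean contrast with the 2-fold rule.** The above-2-fold rule has its own error, up to 24% at SD 1.0 on a continuous scale.

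**Conclusion.** The gap in the definition is real and can be read directly from SAP 10.6.2.1 and 10.6.2.2. For an N-seronegative subject with a measurable baseline and no true change, 50% is the exact per-visit ceiling. On duplicate two-fold dilutions the figure is about 24-40% for an assumed SD of 0.3-1.0 log2. The above-2-fold rule on the same assumptions fires about 0-11% on duplicates and 1-24% on continuous values.

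The consequence for the trial is modest and rests on an unknown share. At 1-10% affected, at most 0.5-5% of controls are misclassified. In the CVnCoV arms, at 10% affected with failures spread evenly at a 95% rate, the inflation is about 0.25 points. It tends to zero if nearly all such recipients truly rise. The documents do not support a reading that the primary seroconversion result as a whole is unreliable: every subject below the cut point at baseline is scored by a sound rule. This is a worthwhile correction to a primary endpoint definition, and no formal inference depends on it.

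**What to change.** In SAP 10.6.2.1 and 10.6.2.2, choose the criterion by the baseline titer in the assay being scored:

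- baseline below the cut point: seroconversion is a post-baseline titer at or above the cut point;
- baseline at or above the cut point: seroconversion is a fold increase above 2, whatever the N status.

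Keep N status for the stratified presentation. Report by arm, for each assay, how many subjects had a measurable baseline; this settles the unknown share. N-seronegative subjects below the cut point are scored as they are now.

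Keep the any-increase result beside the new one. Protocol 9.2.1 defines it for spike, SAP 11.1 records three interim analyses as done, and the sponsor is unblinded (protocol 7.3), so a silent replacement would look data-driven. Record the change in SAP 6.1.

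The cost is one derivation and an extra table row, using data already collected. The stated seroconversion rate in N-seronegative subjects may fall slightly.
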